17.2	Data handling, storage and sharing	94
18.	Dissemination of findings	97
	References	98
19.	Amendments to protocol.....	99
20.	Appendix 1	100

Glossary / abbreviations

ADEM	Acute disseminated encephalomyelitis
AE	Adverse event - any undesirable event in a subject receiving treatment according to the protocol, including occurrences which are not necessarily caused by or related to administration of the research procedures.
AESI	Adverse Event of Special Interest
ALPS	Autoimmune lymphoproliferative syndrome
AR	Adverse reaction - is any undesirable experience that has happened to a subject while taking a drug that is suspected to be caused by the drug or drugs.
ARDS	Acute respiratory distress syndrome
aQIV	Adjuvanted influenza vaccine
BTC	Bristol Trials Centre
CI	Chief investigator
CMI	Cell-mediated immunity
e-CRF	Electronic case report form
CTA	Clinical Trials Authorisation
C19	mRNA bivalent COVID-19 vaccine
DMSC	Data monitoring and safety committee
NHS	National Health Service
NIHR	National Institute for Health Research
GCP	Good Clinical Practice
GDPR	General Data Protection Regulation
GP	General Practitioner
GMC	Geometric Mean Concentrations
GI	Gastrointestinal
HAI	Haemagglutination inhibition assay
HRA	Health Research Authority
HZ	Herpes zoster infection
HZV	Herpes zoster vaccine
ICF	Informed Consent Form
ICS	intracellular cytokine staining
IMP	Investigational Medicinal Product
ISF	Investigator site file
IUD	Intrauterine device
IUS	Intrauterine system
MHRA	Medicines and healthcare products regulatory agency
µg	Microgram
MRC	Medical Research Council
PBMC	Peripheral blood mononuclear cells
PI	Principal Investigator
PIL	Patient information leaflet

pIMD	potential immune mediated disorders
PPI	Patient and public involvement
RCT	Randomised controlled trial
REC	Research ethics committee
RSI	Reference safety information
RZV	Recombinant Herpes Zoster vaccine
SAE	Serious adverse event - events which result in death, are life threatening, require hospitalisation or prolongation of hospitalisation, result in persistent or significant disability or incapacity.
SAP	Statistical analysis plan
SAR	Serious adverse reaction
SSAR	Suspected serious adverse reaction (SSAR) is any serious adverse event that is suspected to be related to the drug or drugs being taken.
SARS-CoV-2	Severe acute respiratory syndrome due to coronavirus
SSR	Solicited systemic adverse reactions
SST	Serum Separator Tube
SOP	Standard operating procedure
SMPC	Summary of Medicinal Product Characteristics
SUSAR	Suspected unexpected serious adverse reaction - an untoward medical occurrence suspected to be related to a medicinal product that is not consistent with the applicable product information and is serious.
TMF	Trial master file
TMG	Trial management group
TSC	Trial steering committee
VRR	Vaccine response rate
UHBW	University Hospitals Bristol and Weston NHS Foundation Trust
UKCRC	UK Clinical Research Collaboration
WHO	World Health Organisation

1. Trial Synopsis

Herpes zoster (HZ) is a vaccine preventable infection with an associated mortality of up to 7%.¹ In the UK vaccination against HZ is recommended for adults on their 70th birthday.² Uptake of HZ vaccine (HZV) is suboptimal therefore strategies to improve uptake are needed. Routine reporting of HZV uptake suggests that uptake is greater during influenza vaccination season.³ It is assumed that increased uptake at this time is due to opportunistic vaccination with HZV when patients attend for influenza vaccination. A recombinant herpes zoster vaccine with adjuvant (RZV) has been recommended in the UK since 2021. Up until May 2023 concomitant administration of RZV with either adjuvanted flu vaccine or COVID-19 vaccine (C-19) was not recommended due to concern about misattribution of side-effects and limited experience with COVID-19 vaccines. The policy was updated in May 2023 to allow co-administration of COVID-19 vaccines with any vaccine. This was based on recent evidence supporting the acceptable safety profile of a COVID-19 vaccine with RZV and to improve timely protection and uptake.⁴ There is still a need however for safety data with co-administration of second dose of RZV as the adverse event profile differs between the doses and there is a lack of published data on the safety and immunogenicity of RZV and adjuvanted flu vaccine.

Figure 1 shows trial schema.

Table 1 Trial synopsis

Trial title	A phase IV, multi-centre, randomised controlled trial to assess immunogenicity and safety of COVID-19 and seasonal influenza vaccine given to healthy adults or those with underlying medical conditions when co-administered with a recombinant herpes zoster vaccine with adjuvant
Internal ref (or short title)	ZosterFluCov

Trial registration	ISRCTN26495549
Sponsor	University Hospitals Bristol and Weston NHS Foundation Trust Research & Innovation Department [name]
Funder	GSK
Clinical Phase	Phase IV
Trial Design	Randomised, controlled, vaccine co-administration study with blinding
Trial Participants	Adults aged 50 and above with or without stable co-morbidities
Sample Size	
A total of 960 participants, consisting of two serology sub-cohorts (COVID-19, n=360; influenza, n=720); cell-mediated immunity (CMI) cohort CD4+ T cells (n=150) and exploratory immunology cohort (n=150). Participants will be randomised in a 1:1:2:2:2 ratio to one of five groups; 120 participants to groups 1 and 2, and 240 participants to groups 3-5. Only 120 participants in group 3 will progress to the second and third vaccination time points required to assess C19/RZV co-administration.
 
 • All five groups will receive two doses of RZV (except participants in group 3 who do not progress after the first vaccination timepoint and will not have any RZV doses as part of the trial) • At the first and second vaccination timepoints, participants will receive two injections (combinations of RZV, C19, aQIV or placebo)

	
 At the final vaccination visit participants will receive one injection (either second RZV, if in the vaccination season aQIV or C19 or placebo)
Planned trial period	
5 months per participant (following from the first study vaccination)
 
6 months for recruitment (following from first participant recruited)
 
28 months including trial set up and close down

	Objectives	Outcome Measures	Timepoint(s)
Co-primary immunogenicity outcomes	Immunogenicity, measured by S-binding total Ig, 1 month-after C19 vaccine given alone compared to co-administration with RZV (first or second dose)	Anti-spike total Ig	Days 0, 28, 56 & 84 Groups 1-3
	Immunogenicity, measured by haemagglutination inhibition assay (HAI), 1 month after aQIV for 3 of the strains included in the vaccine; HAI influenza A H3N2, HAI influenza A H1N1 and HAI influenza B	HAI	Days 0, 28, 56 & 84 Groups 3-5

	Victoria given alone compared to co- administration with RZV		
	Immunogenicity of 2 doses RZV vaccine, 1 month after the second dose, given alone, compared to co-administration with C19 or aQIV with either first or second dose of RZV	Anti-gE Ig	Days 0, 56, 84, & 140 Groups 1-5
Co-primary safety outcomes	Rate of grade 3 and 4 solicited systemic adverse reactions (SSR) over 7 days after 1 st and 2 nd doses of RZV given alone compared to co- administration with C19	Rate of fatigue Fever Gastrointestinal (GI) symptoms [†] Headache Myalgia Shivering	Days 0, 56, 112 Groups 1-5

	Rate of grade 3 and 4, solicited systemic adverse reactions over 7 days after 1 st and 2 nd doses of RZV given alone compared to co-administration with aQIV	Rate of fatigue Fever GI symptoms [†] Headache Myalgia Shivering	Days 0, 56, 112 Groups 1-5
Secondary outcomes	Cell-mediated responses to 2 doses of RZV, 1 month after the second dose, given alone compared to co-administration with C19 with first or second dose of RZV	gE specific T-cells measured by intracellular cytokine staining	Days 0, 56, 84, & 140 Groups 1-5
	Exploratory evaluation of CD4+ T-cells against COVID-19 after vaccination with RZV or aQIV	T-cell Elispot	Day 0 and 28 Groups 1 -3
	N- protein immunoglobulin, before and 1 month after first vaccination in the	N-protein Ig	Day 0, 28 Groups 1-3

	(exploratory immunology cohort)		
	Grade 3 and 4 SSR after 1 st RZV dose in group 1 (day 56), group 2 and 5 (day 0) compared to grade 3 and 4 SSR after 1 st dose of RZV with C19 in group 3 (day 56)	Rate of fatigue Fever GI symptomst† Headache Myalgia Shivering	Day 0 and 56 Groups 1, 2, 3 and 5
	Grade 3 and 4 SSR after 2 nd dose of RZV in group 1 and 3 (day 112) and group 4 (day 56) compared to grade 3 and 4 SSR after 2 nd dose RZV with C19 in group 2 (day 56)	Rate of fatigue Fever GI symptomst† Headache Myalgia Shivering	Day 56 and 112 Groups 1-4
	Grade 3 and 4 SSR after 1 st dose RZV in group 1 (day 56) group 2 and 5 (day 0) compared to grade 3 and 4 SSR after 1 st dose of RZV with aQIV in group 4 (day 0)	Rate of fatigue Fever GI symptomst† Headache Myalgia Shivering	Days 0 and 56 Groups 1,2,4 and 5
	Grade 3 and 4 SSR after 2 nd dose of RZV in group 1	Rate of fatigue Fever	Days 0, 56 and 112 Groups 1, 3 ,4 and 5

	(day 112), group 3 (day 112) and group 4 (day 56) compared to grade 3 and 4 SSR after 2 nd dose RZV with aQIV in group 5	GI symptoms† Headache Myalgia Shivering	
	SSR events over 7 days after 1 st and 2 nd doses of RZV given alone compared to co-administration with either C19 or aQIV	Rate of fatigue Fever GI symptoms† Headache Myalgia Shivering	Days 0, 56 & 112 Groups 1-5
	SSR events over 7 days after 1 st RZV dose in group 1 (day 56), group 2 and 5 (day 0) compared to SSR events over 7 days after 1 st dose of RZV with C19 in group 3 (day 56)		
	SSR events over 7 days after 2 nd dose of RZV in group 1 and 3 (day 112) and group 4 (day 56) compared to SSR events over 7 days after 2 nd dose		

	RZV with C19 in group 2 (day 56)		
	SSR events over 7 days after 1 st dose RZV in group 1 (day 56), group 2 and 5 (day 0) compared to SSR events over 7 days after 1 st dose of RZV with aQIV in group 4 (day 0)		
	SSR events over 7 days after 2 nd dose of RZV in group 1 (day 112), group 3 (day 112) and group 4 (day 56) compared to SSR events over 7 days after 2 nd dose RZV with aQIV in group 5		
	Solicited local adverse reactions over 7 days after 1 st or 2 nd doses of RZV given alone compared to	Frequency and rate of injection site redness, swelling and pain	Days 0, 56 & 112 Groups 1-5

	co-administration with either C19 or aQIV		
	Days off work (for participants in employment) due to vaccine related AEs associated with different schedules under study over a period of 140 days (until study end)	Days missed	Days 0, 56 & 112 Groups 1-5
	Quality of life score over the 7 days after 1 st and 2 nd doses of RZV given alone compared to co-administration with either C19 or aQIV	EuroQol-5D	Days 0 and 7 days after each vaccination Groups 1-5
	AEs up to 30 days after 1 st and 2 nd doses of RZV given alone compared to co-administration with either Bivalent vaccine or aQIV	Frequency and rate of unsolicited AEs	Days 0, 56 & 112 Groups 1-5
	Serious adverse events and AEs of special interest Potential Immune-	Frequency and rate of serious AEs and pIMDs.	All timepoints

	Mediated Diseases (pIMDs) from after 1 st vaccination until end of study		
	Describe participant and study staff attitudes to vaccine co-administration	Semi-structured interviews	Day 112 to 140

Intervention(s)	IMP	Dose	Route of administration
	Shingrix® (GSK) Recombinant subunit herpes zoster vaccine containing AS01 _B (RZV)	0.5ml	Intramuscular
	Comirnaty® Original/Omicron BA.4-5 (15/15 micrograms)/ dose dispersion for injection COVID-19 mRNA Vaccine (nucleoside modified)	0.3ml	Intramuscular
	Adjuvanted Quadrivalent Influenza Vaccine (Surface Antigen, Inactivated) Sequris suspension for injection in pre-filled	0.5ml	Intramuscular

	syringe Influenza vaccine, Adjuvanted with MF59C (aQIV)		
--	---	--	--

[†]GI symptoms include nausea, vomiting, diarrhoea and/or abdominal pai

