4.2 Secondary outcomes

Immunological

- Vaccine response rate (VRR) to RZV as measured by anti-gE, 1 month after vaccination with 2nd dose of RZV, in all groups and between-group differences. VRR defined as a 4-fold increase in post-vaccination anti-gE compared to pre-vaccination anti-gE

concentration for participants who are seronegative at baseline then a 4-fold increase compared to a cut-off value for seropositivity.

- Exploratory evaluation of cell-mediated immunology, CD4+T-cells responses 1 month after the 2nd dose of RZV as measured by intracellular cytokine staining (ICS) compared to RZV given alone or concomitantly for either first or second dose
- S and N-protein immunoglobulin, before and 1 month after vaccination with a single dose of RZV and aQIV to assess for exploratory immunology T-cells against SARS-CoV-2 provided by RZV vaccine or aQIV

Safety

- Percentage of participants reporting grade 3 and 4 SSR after first dose of RZV alone compared to first dose co-administered with either C19 vaccine or aQIV.
- Percentage of participants reporting grade 3 and 4 SSR after second dose of RZV alone compared to second dose co-administered with either C19 vaccine
- Percentage of participants reporting solicited local and systemic Aes, 7 days after each vaccination time point by group and between-group ratios
- Unsolicited Aes for 30 days after vaccination
- Serious adverse events throughout the study period
- Adverse events of special interest (pIMDs) throughout the study period
- Days off work (for participants in employment) during the study period reported as related to vaccination
- Quality of life score following vaccine co-administration compared to single vaccination in the 7 days after vaccination

Qualitative

Outcomes will include but not be limited to

- Participant acceptance of multiple vaccinations (2 or more) for future routine vaccinations
- Trial staff perceptions on offering multiple vaccinations (2 or more) for future routine vaccinations

5. Plan of Investigation

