5.8 Research procedures: participants

Participants will be required to do, or undergo, the following tasks or investigations specifically for the trial which are also outlined in schedule of events (Table 4).

Table 4 Schedule of events

Visit	V1	V2	V3	V4	V5	V6
Timing (days)	D0	D28	D56	D84	D112	D140
Window periods (days)	-	D26-32	D56-60	D82-86	D112-116	D140-146
Eligibility	x					
Urine sample*	x		x		x	

Randomisation	x					
Vaccinations	x		x		X	X**
Bloods (serum) (COVID-19 subset)	x	x	x	x		
Bloods (serum) (Influenza subset)	x	x	x	x		
Bloods (serum) Anti-gE Ig	x		x	x		x
Blood (whole) RZV Cell- mediated immunology (CMI)	x		x	x		x
Blood (whole) exploratory immunity	x	x				
+Diary Card training	x					
Diary Card review						
Safety Review						
Quality of life survey	x		X***		X***	
Missed workdays			x		x	

* Urinary pregnancy testing for female participants of child-bearing potential only**Group 1 will receive the flu vaccine at visit 6 if in the winter vaccination season.

***Quality of life survey completed 7 days after vaccination

Volunteers interested in participating will be asked to complete an ‘expression of interest/initial screening’ questionnaire available via a public website. See section 12.3 for details of how the public will be made aware of the trial.

The ‘expression of interest/initial screening’ questionnaire will assess whether the volunteer meets the key inclusion criteria for participation (e.g. age, received their initial course (usually two doses) of COVID-19 vaccinations). If these criteria are met, they will be asked to indicate their electronic consent to proceed to more detailed screening, and for the research team to contact their GP for further clarification of medical history (if required) and confirmation of vaccination record.

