5.8.10 Visit 5 Safety review, blood sampling and administration of trial vaccine

- Safety review to assess for any serious adverse events
- Review and reconciliation of diary card data submitted
- Assessment for local and systemic adverse reactions and events and medical history since visit 1
- Physical examination (if clinically indicated)
- Measurement of temperature
- Administration of trial vaccines as per randomisation
- Semi-structured interview (optional)* (See section 8 for further details)

5.8.11 Between visit 5 and visit 6

- Complete an electronic diary card for the first 7 days. This diary card will be used to capture:
 - AEs, including their timing and severity
- Report any hospitalisation as soon as is practically possible using the emergency 24-hour telephone number provided
- Report any other urgent medical concerns using the trial centre emergency procedures
- Report any unsolicited adverse events on the electronic diary card between day 8 and day 30 after vaccination
- Complete Quality of Life questionnaire 7 days after vaccination

5.8.12 Visit 6

At this visit, approximately 4 weeks after visit 5, participants will undergo the following:

- Provide blood sample for assessment of RZV vaccine immunogenicity
- Provide blood sample for assessment of cell-mediated immunity against RZV in CMI subset
- Participants randomised to group 1 will receive the flu vaccine if the visit is taking place during the winter vaccination season
- Confirm consent to follow up any clinically significant adverse events after end of participation in the study
- Semi-structured interview (optional) (See section 8 for further details)

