6.10 Duration of treatment period

The duration of the treatment commences when the participant receives their first vaccines as per randomisation and concludes one month after visit 5. For each participant this will be a total of approximately 5 months.

7. Data collection

Each participant will be assigned a unique trial number. Administrative data recorded on paper relating to the participant will be stored securely. Staff with authorisation to make changes to the trial records on the trial database, will be listed on the site delegation log.

Baseline data will be collected after written informed consent. Volunteers will be contacted by an authorised member of the local research or direct care team (as specified in the delegation log) who will provide the opportunity to understand the nature, significance, implications and risks of the trial so that they may make an informed decision if they should take part. If the patient decides to take part the member of the local research or direct care team will obtain informed consent.

Data collection will include the following elements:

- a) A log of all volunteers who express interest in joining the trial and pass the pre-screening eligibility checks.
- b) Volunteers assessed against the full eligibility criteria and, if ineligible, reasons for ineligibility.
- c) Consent information collected prior to randomisation for all participants.
- d) Baseline information (e.g., medical history and assessments) collected for all participating patients.
- e) Data collected from participant diaries completed throughout their participation in the trial.
- f) Data collected at trial visits.
- g) Data derived from analyses of blood samples.

Impact of life measures

This will be assessed using the EQ-5D health survey which participants will be asked to fill in electronically through the platform used for trial management. If participants do not have access to an internet connected device, they will have the option to complete a paper EQ-5D questionnaire.

Diary cards will capture missed time from work by employed participants and caregivers.

8. Integrated Qualitative Research

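### Table 4 schedules missed workdays at visits 3 and 5 only, which does not match the 140-day outcome in Table 1 and section 4.2 or the diary capture in section 7

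*Protocol*

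**What the plan says.** Four places in the protocol bear on how lost work is collected.

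- **Table 1 (secondary outcomes):** "Days off work (for participants in employment) due to vaccine related AEs associated with different schedules under study over a period of 140 days", running to study end, with timepoints Days 0, 56 and 112 for Groups 1-5.
- **Section 4.2:** "Days off work (for participants in employment) during the study period reported as related to vaccination", with no restriction to particular visits.
- **Table 4 (section 5.8):** the row "Missed workdays" is marked under V3 (D56) and V5 (D112) and nowhere else. It has no footnote. The quality of life row is marked at V1, V3 and V5, and its V3 and V5 marks carry the footnote "Quality of life survey completed 7 days after vaccination".
- **Section 7:** "Diary cards will capture missed time from work by employed participants and caregivers".

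The sections on the periods after each vaccination (5.8.3, 5.8.7, 5.8.11) describe the card in the same way. It opens with "Complete an electronic diary card for the first 7 days. This diary card will be used to capture", and the only item listed beneath is adverse events with their timing and severity. After the first week the instruction is "Report any unsolicited adverse events on the electronic diary card between day 8 and day 30 after vaccination". None of these sections mentions work.

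For visit 6, section 5.8.12 lists blood samples, Group 1's in-season flu vaccine, the optional interview and "Confirm consent to follow up any clinically significant adverse events after end of participation in the study". It lists no safety review and no diary reconciliation. Section 1.1 shows a safety review for all participants at visit 6, and section 13.5 makes the primary safety analysis wait until the 7-day diary data have been reviewed at visit 6.

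**The concern.** The outcome compares schedules on lost work over the whole of follow-up, so every arm needs its vaccination periods observed in the same way. RZV is given on different days in different arms. A collection schedule that covers two of the three vaccination periods therefore does not miss the same thing in each arm.

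Group 1 is the only arm in which both RZV doses are given without another active vaccine, so the comparison leans on it. Section 13.4 plans a Poisson regression of days off work. No model can restore days that nobody asked about, and the SAP cannot repair this after the event.

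**Working it through.** No sample size, power or error-rate figure is involved, and the plan gives no expected number of days lost. The check sets the collection schedule against the vaccination days.

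**Inputs.** Vaccination days by group from Table 3:

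| Group (randomised) | D0 | D56 | D112 |
|---|---|---|---|
| 1 (120) | C19 + placebo | RZV + placebo | RZV |
| 2 (120) | RZV + placebo | RZV + C19 | aQIV or placebo |
| 3 (240, of whom 120 continue) | aQIV + placebo | C19 + RZV | RZV |
| 4 (240) | RZV + aQIV | RZV + placebo | C19 or placebo |
| 5 (240) | RZV + placebo | RZV + aQIV | C19 or placebo |

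The active vaccine at D112 in Groups 2, 4 and 5 depends on the winter vaccination season. Collection entries from Table 4 are D56 and D112. The outcome period from Table 1 is 140 days.

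**Step 1: count periods and entries.** There are three vaccination days and two entries. At one entry per period, 3 - 2 = 1 period has no entry, whatever the marks mean.

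**Step 2: if the marks look back.** V3 covers D0 to D56 and V5 covers D56 to D112. Unscheduled: D112 to D140, which is 140 - 112 = 28 days. That period holds:
- one of the two RZV doses in Group 1 and the continuing half of Group 3, 120 + 120 = 240 randomised participants;
- no RZV dose in Groups 2, 4 and 5, 120 + 240 + 240 = 600 randomised participants, but any in-season aQIV (Group 2) or C19 (Groups 4 and 5).

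**Step 3: if the marks mean after that visit's vaccination.** V3 then covers the period after D56 and V5 the period after D112. Unscheduled: the period after D0. That holds the first RZV dose in Groups 2, 4 and 5, including Group 4's co-administration with aQIV, and Group 1's C19 and Group 3's aQIV. Both RZV doses in Group 1 and continuing Group 3 are covered.

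**Step 4: which reading?** The missing footnote on the workdays row, beside a footnoted row, favours look-back. Being marked in the same two post-baseline columns as quality of life leaves the other reading open. The protocol does not settle it.

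**Step 5: add the diary.** If section 7 is applied to the 7-day card, the card covers 3 x 7 = 21 of 140 days, placed alike after D0, D56 and D112 in every arm still in the trial. If the card stays in use to day 30 after D112, it reaches D112 + 30 = D142, beyond nominal study end. Sections 5.8.3, 5.8.7 and 5.8.11 do not list work as diary content for either stretch.

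**Step 6: limits of these counts.** The 240 and 600 are randomised numbers. The outcome applies only to employed participants, whose number is not given. Half of Group 3 leaves at visit 2, so neither Table 4 entry can apply to them.

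**Step 7: visit 6.** Sections 5.8.4, 5.8.8 and 5.8.10 each list a safety review, diary reconciliation and adverse event assessment for visits 2, 4 and 5. Section 5.8.12 lists none of these for visit 6, although 1.1 and 13.5 rely on a safety review and a diary review there.

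**The case against.** The strongest answer is that the diary already does the job. Section 7 names the diary card as the instrument, 5.8.11 requires one after visit 5, and Table 1 lists Day 112 for all groups. The outcome is limited to vaccine-related absence, so the days soon after each injection matter most. The same card is also used for unsolicited events on days 8 to 30, and between visits 2 and 3 and visits 4 and 5 with no day limit stated.

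Much of this stands. A reader might infer from Table 4 that days lost after the D112 RZV dose are left out in Groups 1 and 3, so that co-administration would look costlier in lost work than it is. The documents do not support that. The diary may capture those days, the look-back reading is not stated, the alternative reading moves the gap to other arms, and in season Groups 2, 4 and 5 also receive an active vaccine at D112. Any percentage shortfall would need per-dose losses that the protocol does not give.

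The diary does not remove the conflict, however. The sections that tell sites what the card records mention only adverse events. A 7-day card is not a 140-day count. If the diary were the only instrument, the V3 and V5 marks would have no purpose.

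A second objection is that a missing mark is weak evidence. In the copy read, the Diary Card review and Safety Review rows of Table 4 are empty, so marks may have been lost. Against that, V6 marks survive in the vaccination, anti-gE and cell-mediated immunity rows. The sponsor can check the source table.

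On visit 6, sections 1.1 and 13.5 show that a review is intended. This makes 5.8.12 an incomplete list, not proof that the review will not happen.

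**Conclusion.** The inconsistency holds. Table 4's two entries do not match the 140-day outcome at Days 0, 56 and 112 in Table 1, the whole-study period in section 4.2, or diary capture in section 7. One of three vaccination periods has no entry, and the RZV doses that fall in it differ by arm: D112 doses in Group 1 and continuing Group 3 on one reading, D0 doses in Groups 2, 4 and 5 on the other. Capture could therefore differ by arm if sites follow Table 4 and the diary does not ask about work.

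Whether that produces bias, in which direction and how large, cannot be determined from the protocol. It depends on the meaning of the marks, on what the diary asks, on the number of employed participants and on the share vaccinated in season at D112. The outcome is one secondary measure tied to no success criterion, so this is a minor correction.

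The visit 6 mismatch between 5.8.12 and sections 1.1 and 13.5 is a separate drafting conflict. It deserves attention because 13.5 ties the primary safety analysis to that review.

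**What to change.** 1. Add Missed workdays at V6 in Table 4 and in 5.8.12.
2. Footnote the row with one rule for V3, V5 and V6: days lost since the previous entry, with V3 looking back to D0. The three entries then cover D0 to D140 alike in all continuing groups.
3. State how this count relates to the diary entry in section 7: whether the card asks about work, for how many days after each vaccination, and which source gives the analysed count if both exist. Bring 5.8.3, 5.8.7 and 5.8.11 into line.
4. Separately, reconcile 5.8.12 with 1.1 and 13.5 on the safety review and diary reconciliation at visit 6.

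The cost is one question at a visit already planned, plus wording in the schedule and case report form. It has to be done prospectively, because lost workdays not asked about at the time cannot be reliably recovered at analysis.
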